5.4. Exclusion Criteria

Any of the following conditions will exclude the subject from entering the study:

1. Premature discontinuation from core study LAQ/5062 for any reason.
2. Pregnancy or breastfeeding.
3. Subjects with clinically significant or unstable medical or surgical condition detected or worsened during the core study, which would preclude safe and complete study participation.

Exclusion Criteria For The Open-Label Phase

1. Premature discontinuation from LAQ/5063 active double-blind phase for any reason other than sponsor's request.
2. Pregnancy or breastfeeding.
3. Subjects with clinically significant or unstable medical or surgical condition, detected or worsened during the active double-blind phase of LAQ/5063, which would preclude safe and complete study participation.
4. Use of experimental drugs, immunosuppressive drugs, and/or participation in clinical studies within the period from termination of LAQ/5063 active double-blind phase to the open-label phase (LAQ/5063 OL).
5. Previous treatment with immunomodulators with the exception of laquinimod (including IFN 1a and 1b, Glatiramer Acetate and intravenous [IV] immunoglobulin [IG]) within 2 months prior to entering the open-label phase for those subjects who have a time gap between termination of LAQ/5063 active double-blind phase to the open-label phase (LAQ/5063 OL).

6. Use of corticosteroids within 30 days prior to entering the open-label phase, except for IV methylprednisolone 1 g/day for a maximum of 3 days, in the period from termination of LAQ/5063 active double-blind phase to the open-label phase (LAQ/5063 OL).
7. Use of potent inhibitors of CYP3A4 within 2 weeks prior to open label phase (LAQ/5063 OL) and/or use of fluoxetine one month prior entering the open label phase (LAQ/5063 OL), in the period from termination of LAQ/5063 active double-blind phase to the open-label phase (LAQ/5063 OL) (see list in [Appendix 5](#)).
8. Use of the following substrates of CYP1A2: theophylline and/or warfarin within 2 weeks prior to entering the open-label phase (LAQ/5063 OL), in the period from termination of LAQ/5063 active double-blind phase to the open-label phase (LAQ/5063 OL).
9. Use of amiodarone in the period from termination of LAQ/5063 active double-blind phase to the open-label phase (LAQ/5063 OL).
10. Following the switch to new formulation (capsules), hypersensitivity to: mannitol, meglumine or sodium stearyl fumarate.

Exclusion Criteria for the LAQ/5063 OL open-label phase- further extension (after visit Month 24)

1. Premature discontinuation from LAQ/5063 OL phase prior to completion of 24 months of treatment period.
2. Pregnancy or breastfeeding

Female subjects of childbearing potential who may want to get pregnant in the future, and are interested in re-starting laquinimod treatment following delivery and cessation of breastfeeding, may be able to re-enroll in the study after meeting inclusion/exclusion criteria (see [Appendix 10](#)). Re-enrollment will be permitted on a case-by-case basis. Notwithstanding, Teva is under no obligation to re-enroll such subjects and reserves the right to re-enroll or reject enrolment of such returning subjects for no reason and on its sole discretion. A new informed consent form should be signed before re-enrollment (see [Appendix 10](#)).

6. CONCOMITANT MEDICATIONS

6.1. Allowed Concomitant Medications

Symptomatic MS agents, such as anti-cholinergic and anti-spasmolytic drugs, are permitted at clinically appropriate doses.

Short-term treatment with corticosteroids will be allowed during relapses.

Allowed treatment for relapses is a fixed dose of IV methylprednisolone 1 g/day or oral steroids for a maximum of 5 consecutive days. No tapering off is allowed.

Other medications, excluding those mentioned in Section 6.2, may be given concomitantly as needed for the subject's welfare.

Topical and inhaled steroids are allowed at the discretion of the Investigator for indications other than MS.

Administration of all medications, including indication, dose, frequency and route of administration will be recorded in the source documentation file and in the case report form (CRF).

Unless clinically indicated, any concomitant therapy should remain stable during the study; changes to the concomitant therapy must be recorded in the source document file as well as in the CRF.

Clinical studies have shown laquinimod 0.6 mg to be a strong inducer of CYP1A2. Subjects taking drugs that are metabolized by CYP1A2 (examples listed in [Appendix 6](#)) should be advised that plasma levels of these drugs could decrease when combined with laquinimod. In general, as a precautionary measure, it is recommended to avoid the use of CYP1A2 substrates in clinical trials of laquinimod. Therapeutic alternatives may be considered in the appropriate clinical context. Additional information on concomitant use of laquinimod and CYP1A2 substrates is presented in the laquinimod IB.

Drug-Drug interaction studies have been performed with laquinimod doses of 0.6 mg and 1.2 mg. These studies show that laquinimod at both doses is a weak inhibitor of CYP3A4. Subjects taking drugs that are metabolized by CYP3A4 (specifically those with a Narrow Therapeutic Index listed in [Appendix 6](#)) should be advised that plasma levels of these drugs could increase when combined with laquinimod.

6.2. Disallowed Medications (During Study)

- Natalizumab (Tysabri®)
- Fingolimod (Gilenya)

- IFN- β 1a or 1b
- Dimethyl fumarate (Tecfidera)
- Glatiramer Acetate
- Teriflunomide (Aubagio)
- Alemtuzumab (Lemtrada)
- Cladribine
- Rituximab
- Ocrelizumab
- Atacicept
- Belimumab
- Ofatumumab
- Inducers of CYP3A4 such as rifampin and carbamadizepine (for more examples see [Appendix 5](#)). Use of CYP3A4 inducers may result in reduced laquinimod plasma concentrations and may reduce its effectiveness.
- Moderate/strong inhibitors of CYP3A4; for example, ketoconazole and erythromycin (see full list in [Appendix 5](#)) are disallowed for 2 weeks prior to the baseline visit through to 30 days after the final dose of laquinimod. Laquinimod is extensively metabolized predominantly by CYP3A4, and ketoconazole and fluconazole, strong and moderate inhibitors of CYP3A4, were found to inhibit the metabolism, leading to 2.5- and 3.1-fold increases in laquinimod exposure, respectively.
- Mitoxantrone (Novantrone[®])
- Oral and parenteral steroids (except if given as defined by protocol for relapse; see Section [6.1](#))
- Adrenocorticotropic hormone (ACTH)
- Chemotherapeutic agents
- Cytotoxic agents
- Cyclophosphamide
- IV immunoglobulin (IVIG)

- Plasmapheresis
- Any other experimental agents
- Other immunosuppressive or immunomodulating agents

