3. INTRODUCTION

3.1. Background

3.1.1. General

Multiple Sclerosis (MS) is a chronic, relapsing or progressive, inflammatory demyelinating disease of the central nervous system (CNS), which leads to disability of various degrees and has different progression rates in different patients. Its prevalence rate varies between races and geographical latitude. MS is a common disease, affecting approximately 2,500,000 people world-wide, the majority being in the temperate areas in Europe and North America. Women are affected 1.5-2 times more frequently than men ([EMEA Guideline 2006](#)). There is, as yet, no cure. Treatment has been aimed at controlling symptoms and slowing progression of disease ([Neuhaus et al 2003](#)). Authorized disease-modifying drugs for relapsing-remitting multiple sclerosis (RRMS) given by injection include interferon (IFN)- β 1a (Avonex^{®a}, Rebif^{®b}), IFN- β 1b (Betaseron^{®c}, Extavia^{®d}), glatiramer acetate (Copaxone^{®e}), mitoxantrone (Novantrone^{®f}), and natalizumab (Tysabri^{®g}; for patients non-responsive to other medications). Oral disease modifying treatments for RRMS include fingolimod (Gilenya^{®h}), teriflunomide (Aubagio^{®i}), and dimethyl fumarate (Tecfidera^{®j}). Oral symptomatic treatment with dalfampridine (Ampyra^{®k}) is approved for the improvement of walking in adult patients with MS with walking disability (Expanded Disability Status Scale [EDSS] 4.0-7.0).

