7.1. Study Period

This is a continuation of the LAQ/5062 study as a multinational, multicenter, randomized, double-blind, parallel group study, assessing the safety, tolerability and efficacy of two doses of laquinimod in subjects with RRMS, followed by an open-label phase of laquinimod 0.6 mg daily (LAQ/5063 OL).

Subjects will enter this randomized, two active arms study immediately after completion of the LAQ/5062 core study. The blinding in both, core study (LAQ/5062) and its extension, will be maintained. Subjects will enter the open-label phase after completion of the Termination visit of LAQ/5063 active double-blind phase (completion of the full 36 weeks or as requested by the Sponsor).

The study duration is 36 weeks of double blind treatment (Week 0 [baseline] to Week 36 [termination]) or until the Sponsor's request. The duration of the open-label phase is as long as the Sponsor continues the development of laquinimod 0.6 mg for RRMS.

Subjects will be evaluated at study sites at Baseline (Week 0 / Termination (Week 36) of Core Study LAQ/5062), at Weeks 4, 8, 12, 16, 24, and 36 (Termination visit of LAQ/5063 active double-blind phase (completion of the full 36 weeks or as requested by the Sponsor).

For the Study 5063 open label extension phase, the visits will be at monthly intervals for the first 3 months and at three months intervals for the period of 24 months. Upon completion of the 24 month treatment period visits will be performed at 6 months intervals thereafter, where, for the purpose of this study, a month is 30 days and a visit is defined as X months \pm 7 days.

During the open label phase subjects will be evaluated at study sites for the following scheduled visits:

Baseline (Month 0 / Termination visit of LAQ/5063 active double-blind phase [completion of the full 36 weeks or as requested by the Sponsor]), Month 1, Month 2, Month 3, Month 6, Month 9, Month 12, Month 15, Month 18, Month 21, Month 24, Month 30, Month 36, Month 42, Month 48, Month 54, Month 60 and every 6 months thereafter, until termination (as long as the Sponsor continues the development of laquinimod 0.6 mg for RRMS) or early discontinuation.

Subjects who discontinue treatment for any reason will continue follow-up according to scheduled visits.

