^c Subjects who performed the test evaluation within a window of \leq 30 days, as part of the Termination visit of LAQ/5063 active double-blind phase (completion of the full 36 weeks or as requested by the Sponsor), will not need to undergo another test evaluation

^d Relapse evaluation will be performed in scheduled as well as unscheduled visits as deemed necessary by the Investigator/Coordinator. 25-foot walk is performed with each neurological evaluation

^e For women of child-bearing potential

^f Subjects who performed the test evaluation within a window of \leq 14 days, as part of the Termination visit of LAQ/5063 active double-blind phase (completion of the full 36 weeks or as requested by the Sponsor), will not need to undergo another test evaluation

^g Mandatory phone calls will be performed within 72 hours of the scheduled home pregnancy test

^h A MRI performed within 14 days as part of the termination visit of LAQ/5063 active double-blind phase (completion of full 36 weeks or as requested by the Sponsor) will not need to undergo another MRI scan for Baseline visit of LAQ/5063 OL.

ⁱ MRI scan will be performed within 4 days prior to the visit date.

^j Weight will be measured at baseline and termination visits only.

^k Testing for Factor V Leiden Mutation will be performed within scheduled or unscheduled visits during the open label phase. Carriers. of the mutation will be discontinued from the study

^l All subjects will take the first IMP administration one day post-baseline visit.

^m Accountability only

Table 7: Study Task Flow Sheet for Study 5063 OL (Months 24 onwards)

Procedure/Visit Number	V10	V11	V12	V13	V14	V15	V16	Every 6 months	Termination	Unscheduled Visit
Months	24	30	36	42	48	54	60		Early Discontinuation	Unscheduled visit^a
Informed Consent ^b Signature	X						X			
Inclusion/Exclusion criteria	X									
Concomitant Medications	X	X	X	X	X	X	X	X	X	X
Cardiovascular risk factor assessment and management ^c	X		X		X		X	Every 12 months from Month 72		
ECG	X	X	X	X	X	X	X	X	X	X
Neurological Examination	X	X	X	X	X	X	X	X	X	X
Evaluation of Relapse ^d	X	X	X	X	X	X	X	X	X	X
Ascertaining the use of Effective contraception	X	X	X	X	X	X	X	X	X	X
Serum and urine β-hCG ^e (on site)	X	X	X	X	X	X	X	Serum test only	X	
Urine β-hCG ^e (self check, at home); Pregnancy tests mandatory phone calls ^f	EVERY 1 MONTH BETWEEN VISITS									
Adverse Events	X	X	X	X	X	X	X	X	X	X
MRI (T ₁ , T ₂)	X									
Vital Signs ^g	X	X	X	X	X	X	X	X	X	X

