Physical Examination	X	X	X	X	X	X	X	X	X	X
Safety Laboratory Tests (including inflammatory markers, GFR estimation)	X	X	X	X	X	X	X ^h	X ^h	X ^h	X ^h
Laquinimod Dispensing, & Accountability	X	X	X	X	X	X	X ⁱ	X	X ⁱ	X
Subject Compliance	X	X	X	X	X	X	X	X	X	X
Termination Documentation & Notification of Early Termination								X		

Procedure/Visit Number	V10	V11	V12	V13	V14	V15	V16	Every 6 months	Termination	Unscheduled Visit
Months	24	30	36	42	48	54	60		Early Discontinuation	Unscheduled visit ^a
Unscheduled samples										X ^j

Subjects who are discontinued from study treatment will be encouraged to continue all scheduled visits and procedures until completion of the study (with the exception of procedures associated with drug dispensing and accountability, pregnancy testing, and GFR estimation [including body weight measurement]).

^a Assessments during an unscheduled visit will be performed as deemed necessary by the Investigator, except for vital signs and adverse events, which are mandatory at each visit

^b At Month 24 (visit 10) of the open label phase Informed Consent will be signed for the extended open label period of 36 months. At Month 60 (visit 16) of the open label phase an Informed Consent will be signed for the additional extension as long as the Sponsor continues the development of laquinimod 0.6 mg for RRMS

^c In addition, an evaluation should take place as soon as possible for subjects already in the study, following approval of Amendment #10

^d Relapse evaluation will be performed in scheduled as well as unscheduled visits as deemed necessary by the Investigator/Coordinator

^e For women of child-bearing potential

^f Mandatory phone calls will be performed within 72 hours of the scheduled home pregnancy test

^g Weight will be measured at all visits

^h Inflammatory markers will not be collected from Month 60 and onwards

ⁱ Only drug retrieval

^j Unscheduled urgent safety laboratory samples, pharmacokinetic blood samples, and/or samples for potential biomarker analyses may be collected at the discretion of the investigator or medical monitor at any time to assist with further investigations of cardiovascular events or other clinical event of interest. The samples should be collected as soon as possible in association with the event.

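### Except for CYP3A4 inhibitors, the Section 6.2 bans are tied to the study and not to laquinimod treatment, so read literally they bar other MS drugs and chemotherapy in off-drug follow-up

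*Combined protocol and SAP*

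**What the plan says.** Section 6 is headed "6. CONCOMITANT MEDICATIONS". Section 6.1 gives a general permission that leaves out the banned list: "Other medications, excluding those mentioned in Section 6.2, may be given concomitantly as needed". The list follows under "6.2. Disallowed Medications (During Study"). One entry, moderate/strong CYP3A4 inhibitors, ends by reference to dosing, at 30 days after the final dose.

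Section 3.1.1 names the authorised disease-modifying drugs. Besides the injectables it says "Oral disease modifying treatments for RRMS include fingolimod", and then adds teriflunomide and dimethyl fumarate. All of them appear in Section 6.2.

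On follow-up after stopping drug, Sections 5.1, 7.1 and 7.3.2 say that these subjects stay on the visit schedule. Sections 7.3.3 and 7.3.4, and the note to Table 7 ("Study Task Flow Sheet for Study 5063 OL (Months 24 onwards")), say that they are encouraged to complete all visits and procedures, "with the exception of procedures associated with drug dispensing and accountability, pregnancy testing, and GFR estimation" (with body weight attached to the last item). The period has no fixed end: "The duration of the open-label phase is as long as the Sponsor continues the development of laquinimod 0.6 mg for RRMS". The procedures listed in Section 7.3.2 include a medication review whose stated purpose is to confirm that no disallowed drug is in use.

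Section 11.5.1 tabulates adverse events by treatment group and several other factors. Time on or off drug is not one of them.

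**The concern.** A subject who stops laquinimod permanently will often need something else: another disease-modifying drug or, under the cancer stopping rule in Section 7.3.4.1.3, chemotherapy. That subject is also meant to stay in the study. A site that takes the Section 6.2 heading at its word would treat the new drug as a violation. A site that infers a treatment-period scope would simply record it.

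Two things are at stake. Section 21.1 says that the extra follow-up was added for safety reasons, and subjects who start new treatment could be lost from it at some sites. In addition, Section 10 counts any event after consent as an adverse event, so events during open-ended time on other drugs can fall in the laquinimod 0.6 mg column of the Section 11.5.1 tables.

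**Working it through.** The plan states no figure on this point. The check is a count and a comparison of passages.

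**Count of Section 6.2**
- Entries in the list: 25.
- Entries with an end tied to the last dose: 1 (moderate/strong CYP3A4 inhibitors).
- Entries without one: 25 − 1 = 24.
- Of those 24, entries covering drugs authorised in Section 3.1.1: natalizumab, fingolimod, interferon beta (1a or 1b), dimethyl fumarate, glatiramer acetate, teriflunomide and mitoxantrone. That is 7 entries and 8 drugs, because the interferon entry covers two. All 8 of the 8 drugs named in Section 3.1.1 are covered.
- Of those 24, entries covering cancer-type treatment: chemotherapeutic agents, cytotoxic agents and cyclophosphamide, 3 entries.
- Entries likely to matter to a subject off drug: 7 + 3 = 10 of 24.

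**Does anything lift the bans off drug?**
- Three procedure groups are waived: dispensing and accountability; pregnancy testing; GFR estimation with weight. The disallowed-drug check is not one of them.
- Where the authors wanted an on-drug limit, they wrote it. Section 8.2.3 measures open-label weight only while the subject continues study drug. Section 8.2.5 excuses women off treatment from pregnancy tests. Section 6.2 has no such limit.
- The Section 7.3.4 sentence on customary treatment by the site concerns subjects who leave the study prematurely, and Section 7.3.3 defines early discontinuation as withdrawal from the study. It could be read to cover off-drug subjects who still attend, but it does not mention Section 6.2.

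**Does anything suggest a treatment-period intent?**
- Section 5.3 requires contraception for the study plus 30 days after the last dose. Section 3.4.2.1 gives the same rule as treatment duration plus 30 days.
- Appendix 10, item 2, bars CYP3A4 inhibitors during the study and for 30 days after the last dose, while Table 8 in Appendix 5 gives the period as treatment plus 30 days. The 30-day tail would be redundant if the study period ran on through off-drug follow-up.
- The termination-visit medication review in Section 7.3.3 names only CYP3A4 inhibitors as barred after the last dose.
- Against this, Appendix 5 bars CYP3A4 inducers during the study with no end point.

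The evidence of intent is good, but it is indirect. It comes from passages on contraception, CYP3A4 inhibitors and the termination visit. None of them states when the bans on MS drugs or chemotherapy end.

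**Who is outside the point.** Appendix 10, item 7, removes pregnant subjects from the study and from scheduled follow-up, so the gap does not reach them.

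**The case against.** The strongest reply is that the protocol uses study and treatment interchangeably when it sets drug restrictions, so the Section 6.2 heading already means while on laquinimod. The title of Section 6 and the heading of Section 7.3.2, which refers to treatment visits, point the same way. So do the reasons given for the CYP3A4 entries, which concern laquinimod exposure. Keeping cancer patients in follow-up while barring their treatment would defeat the purpose, and no passage tells a site to withhold it. This stands as evidence of intent, and it is why the point concerns wording and not policy. It does not supply the missing sentence, and Section 7.3.2 itself places off-drug subjects in the visits where the check is made.

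A second reply is that harm is speculative. That largely stands. A reader might infer that starting a banned drug forces a subject out of the study. The documents do not say so: Section 8.3 makes withdrawal discretionary and requires consultation with the sponsor.

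A third reply is that Section 11 is descriptive and built around the 36-week double-blind phase, and that misattribution is limited because onset, action taken, relationship and all medications are recorded and serious events are discussed case by case. That reduces the problem for individual serious cases. It does not separate off-drug time in the summary tables.

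**Conclusion.** The point holds as a cheap improvement. With one exception, Section 6.2 ties its bans to the study and not to laquinimod. Amendment 10 made off-drug time part of the study without adjusting the list or the check. By the letter, 24 of 25 bans continue, and 10 of them cover the authorised MS disease-modifying drugs or chemotherapeutic and cytotoxic agents.

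Three stronger readings are not supported. The bans are not all open-ended, since the CYP3A4 inhibitor ban ends 30 days after the last dose. The sponsor cannot be said to intend to deny treatment off drug, because several passages suggest the opposite. Nor can the 110 subjects ongoing at Amendment 10 be taken as the number affected: the documents do not say how many have stopped or will stop laquinimod, or start a listed drug.

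The conclusion assumes only that some subjects stop permanently, stay in visits and need other treatment, which the stopping rules and follow-up text make plausible.

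**What to change.** - **Section 6.2:** state that the bans apply while a subject is on laquinimod, including temporary interruptions under Section 7.3.5, and end at permanent discontinuation. CYP3A4 inhibitors stay barred to 30 days after the last dose.
- **Section 7.3.2:** limit the disallowed-drug check to subjects on laquinimod.
- **Sections 7.3.3 and 7.3.4:** state that standard MS and cancer treatment in off-drug follow-up is allowed and is not a protocol violation. Section 6.1 already requires the record: "changes to the concomitant therapy must be recorded in the source document file as well as in the CRF".
- **Section 11.5.1:** report open-label adverse events separately for on-drug time, through 30 days after the last dose, and off-drug time. Section 10 already uses 30 days for serious-event reporting. With the half-life of about 80 hours in Section 3.1.2, 30 days is 720 / 80 = 9 half-lives, so about 0.5^9 = 0.2% of the drug would remain.

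The cost is a few sentences and one on-drug/off-drug flag in the analysis data. The downside is that off-drug follow-up will openly include time on other drugs, which the flag keeps apart from laquinimod time.
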